### **Treatment Compliance**

Patients will be asked to return all unused medication at the end of the study and the quantity of returned medication will be documented.

## **8 Evaluation Criteria**

Patients satisfying inclusion criteria will be chosen to participate in the study. The degree of pigmentation will be noted at baseline by mexameter readings taken on both sides of the face on affected skin and also nearby normal skin. Additional mexameter readings will be taken at weeks 2, 4, 8, and 14. In addition standard and polarized photographs will be taken at baseline and at weeks 8 and 14. A MASI score will also be calculated at baseline and at weeks 2, 4, 8, and 14. A melasma severity assessment will be performed by the physician at baseline and at weeks 8 and 14. A physician and patient global assessment will be performed at weeks 8 and 14, a subjective measure of which side, if any, improved more and to what degree (no change/slight/moderate/marked). Primary efficacy assessment will be improvement of melasma using mexameter readings while secondary assessment will be improvement in MASI scores, melasma severity assessment, and physician and patient global improvement compared with the opposite side.

## **9 Off-study criteria**

Safety assessments will consist of monitoring and recording all adverse events, including serious adverse events. An adverse event is any undesirable sign, symptom or medical condition occurring after starting the study drug (or therapy). Medical conditions/diseases present before starting the study treatment are only considered adverse events if they worsen after starting the study treatment. As this study only involves topical therapy, the most likely adverse events are

minor and may include irritation, redness, burning, skin peeling, and hyper/hypopigmentation. These adverse events will be specifically monitored for by using investigator observed evaluation and patient reporting. The patient will be specifically queried upon each visit regarding adverse events from the salicylic acid peels and/or the 4% hydroquinone cream. A patient has the right to discontinue participation in the study at any time. The study investigator also has the right to discontinue the patient's participation in the study should the patient's condition worsen, they are unable to follow the treatment schedule, or the patient has unexpected side effects from the study medications.

A serious adverse event is an undesirable sign, symptom or medical condition which: 1) is fatal or life-threatening, 2) requires or prolongs hospitalization, 3) results in persistent or significant disability/incapacity, 4) constitutes a congenital anomaly or a birth defect, or 5) is medically significant, in that it may jeopardize the subject and may require medical or surgical intervention to prevent one of the outcomes listed above.

All adverse events will be reported to the principal investigator. All unexpected or serious adverse events will also be reported to the IRB.

## **10 Registration and study monitoring**

Once patients are recruited into the study and complete their initial evaluation, they will be given a schedule of follow up visits. As indicated in the schedule above, at each subsequent visit, they will be asked about adverse events, and they will be evaluated by a study investigator. All information will be recorded in the study report forms. All adverse events will be reported to the principal investigator, and all unexpected or serious adverse events will also be reported to the IRB.

## **11 Statistical Considerations**

Investigators will enter the information required by the protocol into the Study Report Forms (SRFs). Additionally, a series of standardized photographs will be taken of each patient at baseline and 14 weeks to provide permanent documentation.

The objective of this trial is to study the efficacy and tolerability of salicylic acid peels in the treatment of melasma in Hispanic women. The data will be summarized with respect to efficacy and safety observations. Data will be presented for the complete intent-to-treat population (all patients having taken at least one dose of study medication) as well as the per-protocol population (all patients who completed the study without major protocol deviations).

The assessment of safety will be based mainly on the frequency of adverse events, which includes all serious adverse events. Adverse events will be summarized by presenting for each treatment group the number and percentage of patients having any adverse event, having an adverse event in each body system, and having each individual adverse event. Any other information collected (e.g. severity or relatedness to study medication) will be listed as appropriate.

Efficacy will be primarily assessed by comparing delta mexameter readings (affected skin-nearby normal skin) on the peeled versus unpeeled side. This data will be analyzed using a two factor repeated measures analysis of variance. Efficacy will be secondarily assessed by change in MASI score on the peeled versus unpeeled side also using the repeated measures analysis of variance. Another secondary measure of efficacy will be the melasma severity assessment of the peeled versus unpeeled side also using the repeated measures analysis of variance.

A McNemar chi-squared test will be used to determine if there is agreement between the Physician and Patient Global Assessment of Improvement at 8 and 14 weeks as to which side appears more improved. For those in which there is agreement, we will further look at the degree of agreement and use the McNemar chi-squared test to see how well they correlate. The critical value for all efficacy, tolerability, and subject satisfaction survey analyses will be 0.05.

A previous study has shown that using 4% hydroquinone cream alone results in total improvement in melasma in ~40% of patients (4). However, the assessments of melasma improvement were more subjective than objective in nature and differ from the end points we are using in our study. Furthermore, it is unclear how much more improvement we may see with the addition of the salicylic acid peels. Since we do not know how much improvement to expect given our efficacy endpoints, we will be performing a pilot study recruiting ~20 patients.

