## 2 Study Objectives

To assess the efficacy of salicylic acid peels every two weeks in combination with 4% hydroquinone versus 4% hydroquinone alone in the treatment of melasma in Hispanic women. This study will take place over 14 weeks in which time all patients will use 4% hydroquinone cream to the affected areas twice daily, but half the face will receive four salicylic acid peels every two weeks. End points include change in pigmentation of skin affected by melasma compared to normal skin measured objectively with a mexameter and subjectively by the MASI score, the melasma severity assessment, and the physician and patient global evaluation.

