#### **4 Agents**

The two agents used in this study will be salicylic acid 20-30% peels and 4% hydroquinone cream, both of which are FDA approved for melasma.

The 4% hydroquinone cream will be purchased as a generic cream formulation. Patients will apply this cream twice a day to affected areas on both sides of the face. Contraindications to the use of 4% hydroquinone include pregnancy, plans for pregnancy, or breast feeding (in all cases patients will be excluded from our study). Side effects can include irritation, redness, pruritus, and hypo/hyperpigmentation. One study comparing the use of 4% hydroquinone with placebo found no significant difference between the two groups in terms of incidence of side effects (4).

The salicylic acid peels will also be purchased from a medical supply company in both 20% and 30% concentrations. Patients will receive 4 peels total at 2 week intervals. The first two peels will be 20% and the last two peels will be 30%. Side effects may include redness, irritation, pruritus, skin peeling, and hypo/hyperpigmentation. One study looked at the safety and efficacy of salicylic acid peels in darker racial-ethnic groups and found the above mild side effects to occur in ~16%, all of which were transient, resolving in less than two weeks (3).

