## **6 Material and data to be accessioned**

Thirty adult Hispanic women with moderate to severe melasma, diagnosed by clinical criteria, will be recruited to participate in this study. Accounting for ~ 10 screening failure, we hope 20 patients will be able to complete this 14 week prospective investigator blinded, split-face trial of biweekly salicylic acid peels in combination with 4% hydroquinone versus 4% hydroquinone alone.

At the initial visit, patients will be asked for their past medical history, current medications, and will undergo a urine pregnancy test. Once it is determined that patients are eligible for the study, they will be asked to give informed written consent and sign a HIPAA authorization. Next they will undergo evaluation of their melasma by the study investigator which includes an objective measurement of the darkness of their melasma by mexameter (an electronic device which painlessly measures skin pigmentation, 0-white, 1000-black, by placing a probe on the skin) compared to nearby normal skin. In addition, a MASI score will be calculated (a subjective score based on darkness, area of involvement, and homogeneity of the pigment). A melasma severity assessment will also be performed by the physician which rates the severity of the melasma on each of side of the face according to the following numerical scale: 0 for clear, 1 for mild, 2 for moderate, 3 for severe. Standard and polarized photographs (a specialized photograph that enhances the appearance of hyperpigmentation) will also be taken. Patients will then undergo a 20% salicylic acid peel to half the face (side to be peeled will be determined by a computer generated randomization code). In addition they will be given 4% hydroquinone to use on the affected areas twice a day (X 14 weeks) and a cleanser and sunscreen to be used daily. No other medications for melasma will be allowed during the study period.

At week 2, patients will undergo another 20% salicylic acid peel to half the face. They will be asked to report any adverse events from the salicylic acid peels or the hydroquinone. Prior to the peel a mexameter reading will be taken and the MASI score calculated for each side of the face.

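### Adverse events are to be tabulated by treatment group in a split-face trial that has no patient groups, the plan does not require the side of a local reaction, and blinded scoring is not placed before adverse event questions

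*Combined protocol and SAP*

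**What the plan says.** On safety tables, Section 11 (Statistical Considerations) reads: "Adverse events will be summarized by presenting for each treatment group the number and percentage of patients having any adverse event". The same counts follow by body system and by individual event. Severity or relatedness is to be listed if it has been collected. Section 11 names tolerability alongside efficacy as the trial objective and applies 0.05 to tolerability analyses, but it names no tolerability comparison. Section 2 is narrower: "To assess the efficacy of salicylic acid peels every two weeks in combination with 4% hydroquinone versus 4% hydroquinone alone".

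On design, Section 4 says of the hydroquinone: "Patients will apply this cream twice a day to affected areas on both sides of the face". Section 7 assigns peels to one half of each face, with the side chosen by a randomization code. The efficacy paragraph of Section 11 accordingly compares the peeled with the unpeeled side.

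On expected reactions, Section 4 says of the cream: "Side effects can include irritation, redness, pruritus, and hypo/hyperpigmentation". Of the peels it says: "Side effects may include redness, irritation, pruritus, skin peeling, and hypo/hyperpigmentation". It adds that a placebo-controlled study of the cream "found no significant difference between the two groups in terms of incidence of side effects", and that a peel study "found the above mild side effects to occur in ~16%, all of which were transient, resolving in less than two weeks".

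On collection, Section 9 has patients asked at every visit about events from the peels and/or the cream, together with observation by the investigator.

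On blinding, Section 7 blinds the investigators only; patients and the nurse who does the peels know the side. After Day 1, the only stated order is at week 2: "Prior to the peel a mexameter reading will be taken and the MASI score calculated for each side of the face".

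**The concern.** The adverse event table is worded for a parallel-group trial. Here the randomised factor is the side of the face, so the tolerability contrast that the design can give is peeled against unpeeled within the same woman. The table as worded does not give that contrast, and the plan does not require the item that would allow it. The side of a redness or irritation that clears within days is hard to recover later if it was not noted at the visit.

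The order of events within a visit is a smaller, separate matter. MASI, the melasma severity assessment and the physician global evaluation are subjective and depend on a scorer who does not know the peeled side. If the patient describes a one-sided reaction before scoring, that protection is lost for the visit and possibly for later ones.

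**Working it through.** The documents state no figure on this point that could be reproduced. The check is a reading of the text, followed by a short calculation of scale.

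**1. Who is in each column.** Section 6 hopes for 20 completers. Sections 4 and 7 expose all of them to the cream and all of them to peels.

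| Reading of treatment group | Patients in each column | What it needs |
|---|---|---|
| Literal groups of patients | the same 20 and the same 20 | nothing; the columns are identical |
| By therapy (peel, cream) | the same 20 and the same 20 | a judged cause for each event |
| By side (peeled, unpeeled) | the same 20 and the same 20 | the side of each local reaction |

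Only the third reading gives the randomised comparison. Non-local events cannot be placed in it at all.

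**2. Is side required?** The text on adverse events is in Sections 6, 9, 10 and 11. It covers when patients are asked, which agent is asked about, that information goes on the report forms, and severity or relatedness where collected. Side is not mentioned.

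**3. Can agent stand in for side?** Section 4 lists irritation, redness, pruritus and hypo/hyperpigmentation for both agents. Skin peeling is listed for the peels only. An event attributed to the peel does imply a side, but for the shared reactions that attribution is a judgement, made by a patient who knows which side was peeled.

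**4. Can other data supply the side?** Peels are at weeks 0, 2, 4 and 6. After baseline, Section 8 has photographs at weeks 8 and 14. The gaps from each peel to the next photograph are 8 − 0 = 8, 8 − 2 = 6, 8 − 4 = 4 and 8 − 6 = 2 weeks. The cited peel reactions cleared in less than two weeks, so no photograph falls inside that time. Mexameter readings by side could partly locate a lasting pigment change, but not a transient reaction.

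**5. Scale.** Inputs: 20 patients (Section 6) and about 16% (Section 4, another study's rate, assumed here to be per patient).
- Expected patients with a peel reaction: 20 × 0.16 = 3.2, or about 3.
- Chance of at least one: 1 − 0.84^20 = 0.969.
- Exact (Clopper-Pearson) 95% interval for 3/20: 3.2% to 37.9%.
- Exact McNemar test with all m discordant patients on one side: p = 2 × 0.5^m, which is 0.0625 for m = 5 and 0.031 for m = 6. Six are therefore needed for p < 0.05.
- Chance of at least 6 of 20, if every reaction is on the peeled side only: 0.087 at 16%; at assumed rates of 10% and 30% it is 0.011 and 0.584.

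A test at 0.05 has little to offer at the cited rate; a description by side is the realistic output.

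**6. Order within visits** (Sections 1 and 6).

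| Visit | Peel | Scoring | Scoring before peel? | Scoring before adverse event questions? |
|---|---|---|---|---|
| Day 1 | yes | yes | yes | no earlier peel to report |
| Week 2 | yes | yes | yes | not stated |
| Week 4 | yes | yes | not stated | not stated |
| Week 6 | yes | no | no scoring | no scoring |
| Week 8 | no | yes | no peel | not stated |
| Week 14 | no | yes | no peel | not stated |

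The order is open at four visits for the questions and at one visit for the peel.

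**The case against.** The strongest reply is that the table can be filled by therapy. Section 7 names an investigational and a reference therapy, and Section 9 asks about events from each. A peel goes on one side only, so an event attributed to it has a known side, and Section 4 reports no significant excess of side effects for the cream over placebo. This stands in part: attribution carries some information. But it gives a judged cause rather than a count on each side, and it is weakest for the reactions that both agents share. A non-significant comparison with placebo is not a rate for the cream.

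A reader might infer that side will not be collected, or that the sides cannot be compared. The documents do not support that. The report forms are not shown and may hold a side field, and investigators are to observe these reactions. The supported statement is that the plan does not require side.

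A reader might also infer that visible redness or peeling will regularly unblind the scorer. The scheduled scoring visits follow the preceding peel by at least two weeks, and the cited reactions cleared sooner. The spoken report is the main route. The week 4 order is a gap in wording: Section 6 requires the investigator to be blind at that visit, which is hard to meet after a fresh peel but is not spelled out.

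Finally, this is a pilot, and by-side counts will be imprecise. That is a reason to describe rather than test. It is not a reason to leave the side unrecorded.

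**Conclusion.** The point holds as a mismatch between a stated reporting rule and the design. The plan does not ensure a peeled-versus-unpeeled comparison of local tolerability, although Section 11 makes tolerability part of the objective. Severity is minor to moderate.

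The only size that the documents support is about 3 of 20 patients with a peel reaction. This assumes that the cited 16% is a per-patient rate and carries over to this trial. It may be tempting to state how large a difference between sides could be hidden. The documents give no cream rate and no split by side, so no such bound can be derived.

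The blinding gap is secondary and of unknown size. It touches MASI, the severity assessment and the physician global evaluation. It should not be read as undermining the primary endpoint: the mexameter reading is instrumental and less exposed. The patient global evaluation is unblinded by design.

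**What to change.** 1. **Sections 9 and 11, recording.** Record each local reaction as left, right, both or not facial, with severity on each side, on a page that the scorer does not see. The nurse, already unblinded, completes it at the four peel visits. At weeks 8 and 14 the patient completes it herself after scoring. Amend the wording on who observes (Section 9) and who enters data (Section 11) to match.
2. **Section 11, table.** Replace the split by treatment group with a descriptive within-patient table of local reactions: peeled only or worse, unpeeled only or worse, both equally, neither. Show it by visit and overall, with exact 95% intervals, so that different visits and the two peel concentrations are not seen only in merged form. Count non-local events once per patient with no group split. Take this table out of the 0.05 rule.
3. **Sections 6 and 9, visit order.** Complete blinded scoring before adverse events are asked about and, at week 4, before that day's peel.

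Reporting of events to the principal investigator and the IRB stays as it is.

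The cost is one form page, a fixed visit order and revised wording; the page for patients would also be needed in Spanish, since Section 5 admits Spanish-speaking women. Some exposure remains: a reaction that is still visible, or an earlier report that the scorer has heard, can still unblind. The documents do not say whether the principal investigator, who receives all event reports, also scores.

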### **Interruption or Discontinuation of Treatment**

Every patient has the right to discontinue study participation at any time, and every patient may be discontinued from the study for any reason beneficial to his/her well being. All data generated up to the time of discontinuation from the study will be analyzed and the reason(s) for discontinuation will be recorded.

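### Section 11 leaves the use of baseline and the deciding term of the primary mexameter ANOVA undefined; adjust for the baseline side difference and name one post-baseline contrast.

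*Combined protocol and SAP*

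**What the plan says.** The primary analysis is two sentences in Section 11: "Efficacy will be primarily assessed by comparing delta mexameter readings (affected skin-nearby normal skin) on the peeled versus unpeeled side", then "This data will be analyzed using a two factor repeated measures analysis of variance". Delta is defined there as a difference between skin sites at one visit, not a change over time. For the secondary endpoint the wording differs: "Efficacy will be secondarily assessed by change in MASI score on the peeled versus unpeeled side".

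Section 8 gives the collection schedule. Pigmentation "will be noted at baseline by mexameter readings taken on both sides of the face", and "Additional mexameter readings will be taken at weeks 2, 4, 8, and 14". It also states: "Primary efficacy assessment will be improvement of melasma using mexameter readings". Section 2 speaks of change in pigmentation. Both point towards a comparison with baseline, but neither says how it is made.

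On incomplete patients, the discontinuation paragraph of Section 7 says "All data generated up to the time of discontinuation from the study will be analyzed". Section 11 promises results for "the complete intent-to-treat population (all patients having taken at least one dose of study medication") and for a per-protocol population. It gives no rule for a patient who lacks some readings.

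**The concern.** Side and visit are the natural two factors, and the visits collected are clear. Two things are open: the role of the baseline reading, and which term of the ANOVA decides.

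The side to be peeled is randomised and baseline precedes any peel, so the expected baseline side difference is zero. Kept as a response level, baseline pulls the side effect towards zero. Subtracted, it adds its own noise. Used as a covariate, it removes noise when visits are correlated. If side by visit decides, the F test yields no single effect estimate.

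This matters because the last paragraph of Section 11 makes the trial a pilot on the ground that the size of the effect is unknown. A defined estimate with its confidence interval is therefore a main product.

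A conventional repeated measures ANOVA also needs every reading from a patient, which sits badly with the promise in Section 7 to analyse all data up to discontinuation.

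**Working it through.** **Inputs from the documents.** Readings on both sides at baseline and weeks 2, 4, 8 and 14 (Section 8); about 20 patients (Sections 6 and 11); critical value 0.05 (Section 11). No SD, correlation, effect size or power is given, so there is no stated figure to reproduce beyond 30 recruited - 10 screening failures = 20.

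**Assumptions.** 20 patients with complete data; peeled-minus-unpeeled difference in delta with SD 1 at each visit; equal correlation r between visits; normal data; two-sided 0.05.

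**Shrinkage if baseline is a response level.** With post-baseline mean effect m, the five-reading side effect is (0 + 4m)/5 = 0.8m, whatever the time course.

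**Variances for the four-visit mean.**
- Unadjusted: [(1+3r)/4]/20.
- Change from baseline: [(1+3r)/4 + 1 - 2r]/20.
- Adjusted for baseline, at zero baseline difference: [(1+3r)/4 - r²]/20 × (1 + 1/17). The last factor is the price of estimating the slope.
- Five readings including baseline: [(1+4r)/5]/20, with the SE multiplied by 1.25 to undo the 4/5.

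Example at r = 0.5: adjusted √[(0.625 - 0.25)/20 × 18/17] = 0.141; change √[(0.625 + 1 - 1)/20] = 0.177; unadjusted √(0.625/20) = 0.177.

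| SE at r = | 0 | 0.3 | 0.5 | 0.7 |
|---|---|---|---|---|
| Adjusted, four visits | 0.115 | 0.143 | 0.141 | 0.123 |
| Unadjusted, four visits | 0.112 | 0.154 | 0.177 | 0.197 |
| Change, four visits | 0.250 | 0.209 | 0.177 | 0.137 |
| Five readings, rescaled | 0.125 | 0.185 | 0.217 | 0.244 |
| Adjusted, weeks 8 and 14 | 0.163 | 0.172 | 0.163 | 0.138 |

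The last row uses [(1+r)/2 - r²]/20 × 18/17.

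**Break-even.** For the four-visit mean, adjusted equals unadjusted when 18r² = (1+3r)/4, that is 72r² - 3r - 1 = 0, so r = (3 + √297)/144 = 0.14. Against change, the adjusted variance is smaller unless (1+4r)/68 > 1 - r, that is r above 67/72 = 0.93.

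**Patient equivalents.** 20 × (unadjusted variance / adjusted variance) gives about 23/31/51 patients at r = 0.3/0.5/0.7 for the unadjusted mean to match 20 with adjustment.

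**Which contrast.** Simulated power with a full effect of 0.66 SD (assumed), at r = 0.3/0.5/0.7. Both means are baseline-adjusted; side by visit uses all five readings. Simulation error is about one point.

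| Time course | Mean of 2, 4, 8, 14 | Mean of 8, 14 | Side by visit |
|---|---|---|---|
| Effect only from week 8 | 60/60/72% | 95/97/99% | 87/96/100% |
| Immediate, gone by week 14 | 91/91/97% | 45/48/62% | 87/96/100% |

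Under the null the adjusted four-visit test rejects about 5%.

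**Incomplete patients.** If 2/5/10% leave before each of the four post-baseline visits (assumed), 1 - 0.98⁴, 1 - 0.95⁴ and 1 - 0.90⁴ give 8/19/34% lacking at least one reading. A complete-case ANOVA drops them.

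**The case against.** The strongest objection is that Sections 2 and 8 already define the endpoint as change or improvement, so the side effect over all five readings fits the protocol worst. That stands. The 4/5 shrinkage is a risk under one reading of Section 11 and a known factor that could be rescaled. A reader might infer that the planned estimate is attenuated; the documents do not commit the sponsor to that analysis. Taking the objection at its word leads to change from baseline, where the loss is one of precision.

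Second, a four-visit mean is not obviously the right target. Week 2 is read before the second peel and half the weight falls on weeks 2 and 4. The power table shows that either mean can lose heavily to the other, and either can lose to side by visit. This also stands: the time course is not in the documents, so the choice belongs to the sponsor.

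Third, a mixed model is not essential for about 20 patients. With complete data, a regression of the mean side difference on the baseline difference is enough. Nor does the mixed model rescue everyone: a patient who leaves before week 2 is in the intent-to-treat population but contributes nothing to a post-baseline contrast.

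A reader might also infer an inflated error rate. If success could be claimed on either the side effect or side by visit, type I error would be about 10% (1 - 0.95² = 0.0975 if independent). Section 11 does not say that either may count, so this is a reason to name one term and not a fault of the plan as written.

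**Conclusion.** The point holds as a missing specification for which a better method is available at almost no cost. Section 11 does not fix the role of baseline or the deciding term, and no other section does.

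Under the stated assumptions, adjustment for the baseline side difference is more precise than change from baseline at every r tabulated, and more precise than the unadjusted post-baseline mean once r exceeds about 0.14. Near r = 0 the loss is negligible. These sizes are illustrative, since the documents give neither an SD nor a correlation.

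Two stronger conclusions are not supported. The test is not biased: each single candidate test, chosen in advance, holds its level under these assumptions. And the trial is not shown to be underpowered: it is a pilot with no stated power, so no target is missed.

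**What to change.** In Section 11:
- Keep baseline out of the response. Adjust for the baseline peeled-minus-unpeeled difference in delta mexameter and estimate the effect at zero baseline difference.
- Before data are seen, name one primary contrast: the mean side difference over weeks 2, 4, 8 and 14, or over weeks 8 and 14. Give the reason for the choice. Test it two-sided at 0.05 and report a 95% confidence interval. Treat side by visit as supportive.
- With complete data, regress the mean side difference on the baseline difference. With missed visits, fit a mixed model to the side differences so that patients with some post-baseline readings contribute, in line with Section 7. Report the number with no post-baseline reading.
- Apply the same approach to MASI. State that MASI is scored per side at baseline; Section 6 says so for week 2 but not for baseline.
- State the same items for the melasma severity assessment, whose only post-baseline visits are weeks 8 and 14.

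The cost is wording and a simple model. The mexameter readings are already planned on both sides; per-side baseline MASI is the only scoring that needs to be made explicit. The price is a slight loss of precision if r is near 0, and less power than side by visit for some time courses.

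### McNemar's test measures neither agreement nor correlation between physician and patient, and neither global assessment has a peeled-versus-unpeeled analysis

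*Combined protocol and SAP*

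**What the plan says.** Section 2 (Study Objectives) lists the physician and patient global evaluations among the end points. Section 8 (Evaluation Criteria) describes the rating, done at weeks 8 and 14, as "a subjective measure of which side, if any, improved more and to what degree (no change/slight/moderate/marked", and places it among the secondary efficacy assessments: "physician and patient global improvement compared with the opposite side".

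Section 11 (Statistical Considerations) gives a repeated measures analysis of variance for mexameter and for MASI, then adds "Another secondary measure of efficacy will be the melasma severity assessment of the peeled versus unpeeled side", analysed the same way. For the global assessments it says only:

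- on side: "A McNemar chi-squared test will be used to determine if there is agreement between the Physician and Patient Global Assessment of Improvement";
- on degree: "For those in which there is agreement, we will further look at the degree of agreement", where the method named for this second step is to "use the McNemar chi-squared test to see how well they correlate".

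Two general statements also apply: "The data will be summarized with respect to efficacy and safety observations" and "The critical value for all efficacy, tolerability, and subject satisfaction survey analyses will be 0.05". Section 7 (Treatments) says that the investigators are blinded and the patients are not.

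**The concern.** There are three faults, the third being the most serious.

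1. **Wrong test for the question.** McNemar's test asks whether two raters choose a category equally often. It uses only the discordant pairs, and its p-value depends heavily on the direction in which they fall. A non-significant result could be reported as agreement when the raters agree no better than chance. A significant one could be reported as disagreement when most patients are rated alike.
2. **Wrong table.** The test needs two categories per rater. The side rating allows three answers (peeled, unpeeled, neither) and the degree scale has four terms. No collapsing rule is given, so one could be chosen after the data are seen.
3. **No efficacy analysis.** Two named efficacy measures have no pre-specified estimate, interval or test of one side against the other. Agreement between raters cannot supply it, because both could agree that the unpeeled side did better. The blinded physician's direct comparison of the two sides is among the measures left without a planned estimate.

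Because patients know which side was peeled, the two raters' side preferences may well differ. McNemar's test would respond to such a difference, but the plan does not use it for that purpose.

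**Working it through.** **Inputs.** From the documents: about 20 patients (Sections 6 and 11), critical value 0.05 (Section 11; sidedness not stated, two-sided assumed here), and the rating categories (Sections 6 and 8). The plan gives no expected ratings and no power for these measures, so there is no figure to reproduce. Every table and rate below is an assumed illustration.

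**Formulas.** Let a = both favour peeled, b = physician only, c = patient only, d = both favour unpeeled, and n = a + b + c + d.

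- McNemar: χ² = (b − c)²/(b + c); the exact version is a two-sided binomial test on b + c at 0.5.
- Agreement: p_o = (a + d)/n.
- Kappa: (p_o − p_e)/(1 − p_e), with p_e = [(a + b)(a + c) + (c + d)(b + d)]/n².

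**Step 1: two outcomes, n = 20.**

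| a/b/c/d | Agreement (exact 95% CI where computed) | Kappa | McNemar p |
|---|---|---|---|
| 0/10/10/0 | 0% | −1.00 | 1 |
| 5/5/5/5 | 50% (27% to 73%) | 0.00 | 1 |
| 10/0/0/10 | 100% | 1.00 | χ² is 0/0; exact p = 1 by convention |
| 10/6/0/4 | 70% (46% to 88%) | 0.40 (95% CI 0.08 to 0.72) | 0.014 uncorrected, 0.031 exact |

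For the last row: p_o = 14/20 = 0.70; p_e = (16×10 + 4×10)/400 = 0.50; kappa = 0.20/0.50 = 0.40; χ² = 6²/6 = 6; exact p = 2×0.5⁶ = 0.031. Total disagreement, chance agreement and perfect agreement are all non-significant, while a table with moderate agreement is significant.

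**Step 2: true agreement fixed, direction of disagreement varied.** Exact enumeration over b, c and the concordant count gives the probability of a non-significant result, uncorrected (exact):

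| True agreement | Disagreements split 50/50 | Split 80/20 |
|---|---|---|
| 50% | 96% (98%) | 53% (63%) |
| 70% | 95% (99%) | 70% (85%) |

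With an even split, agreement of 50% and of 70% give almost the same result. The direction of disagreement moves the result far more than its amount.

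**Step 3: three outcomes.** Rows are the physician and columns the patient, in the order peeled, neither, unpeeled: 9,0,0 / 5,3,0 / 2,0,1.

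- Agreement = (9 + 3 + 1)/20 = 65% (41% to 85%).
- p_e = (9×16 + 8×3 + 3×1)/400 = 0.4275; kappa = (0.65 − 0.4275)/0.5725 = 0.39 (0.09 to 0.69).
- Neither pooled with unpeeled: 9/0/7/4, exact p = 2×0.5⁷ = 0.016.
- Neither pooled with peeled: 17/0/2/1, exact p = 0.50.
- Patients with any rating of neither left out: 9/0/2/1 (12 remain), exact p = 0.50.

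The unstated collapsing rule decides significance.

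**Step 4: the efficacy question in the same table.** The physician favours the peeled side 9 to 3: sign test p = 0.146, and 9/20 = 45% (23% to 68%) of all patients. The patient favours it 16 to 1: p = 0.0003, and 16/20 = 80% (56% to 94%). Neither the agreement rate nor kappa conveys this.

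**Step 5: what a sign test could detect.** If 80% of stated preferences favour the peeled side, two-sided exact power at 0.05 is:

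| Stated preferences | Needed for one side | p at that count | Power |
|---|---|---|---|
| 20 | 15 | 0.041 | 80% |
| 18 | 14 | 0.031 | 72% |
| 16 | 13 | 0.021 | 60% |
| 14 | 12 | 0.013 | 45% |

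**The case against.** The strongest defence is that little would be lost in practice. Section 11 goes on to the patients on whom the raters agree, so the raw number agreeing must be counted. The promise to summarise efficacy data could also yield counts by preferred side. The study is a pilot, and rater agreement is not among its objectives. This limits the harm but does not remove it. No interval, chance-corrected statistic or between-side estimate is named, although the same section names an analysis for each of the other three measures and applies 0.05 to all efficacy analyses.

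On the table structure, no change may simply mean neither side. Patients whose raters agree on a side would then have three degree levels, not four. McNemar may also be loose wording for a multi-category extension. Both readings are possible, but three levels are still not a 2×2 table, and an extension such as Stuart-Maxwell would still test marginal totals, not agreement.

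The illustrations are constructed, and some put every disagreement in one direction. They show what can happen, not what is likely.

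That the physician giving the global rating is blinded follows from the general statement in Section 7; it is not stated for that rating specifically. Section 9 has investigators observing adverse events such as skin peeling, which might reveal the side. This calls for some caution in leaning on that rating.

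**Conclusion.** The point holds. Followed exactly, Section 11 produces p-values that do not answer its stated questions about agreement and correlation, and it leaves two named secondary efficacy measures without a between-side analysis. The missing efficacy analysis is the weightier half.

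The fault in the test follows from what McNemar's test measures and does not depend on the assumed tables; those show only how far the p-value can depart from the agreement. The missing analysis follows from comparing Sections 2 and 8 with Section 11. The effect is limited to the two global assessments in a pilot of about 20 patients. This should be fixed before analysis, but it does not threaten the primary result.

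**What to change.** Reword the global-assessment paragraph of Section 11.

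1. **Agreement.** Replace both McNemar tests with percent agreement and an exact 95% interval as the lead statistic, plus kappa on the three-outcome side rating with its 95% interval, in all rated patients. For side and degree combined, use weighted kappa with named weights. State that intervals will be wide and that kappa can be low when one side dominates: 18/1/1/0 has 90% agreement (68% to 99%) but p_e = (19×19 + 1×1)/400 = 0.905, so kappa = (0.90 − 0.905)/0.095 = −0.05. Keep McNemar or Stuart-Maxwell only as a check of rater bias, with any collapsing rule stated.
2. **Efficacy.** For each rater, report the proportion favouring the peeled side with an exact 95% interval. An exact sign test may be added, or a signed-rank test if the form is confirmed to grade the difference between sides. Name week 8 or week 14 as the main time point; the plan ranks neither. State how ratings of neither side are handled, for example left out of the sign test but kept in the denominator of the proportion.
3. **Optional.** Treat the physician's rating as the main one and label the patient's as unblinded and supportive. State that there is no multiplicity adjustment and that these p-values are exploratory.

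**Cost.** Wording in Section 11 and possibly a clarification of the rating form; no extra data, visits or staff. Power is modest if many ratings favour neither side. Two unadjusted tests carry a false-positive chance of up to 10% (1 − 0.95² = 9.8% if independent); four tests, if both weeks are tested, up to 20% (1 − 0.95⁴ = 18.5%). Leading with estimates and intervals avoids leaning on those p-values.
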